During the OL period, in addition to the TB screening described above, laboratory tests (hematologic and chemical analysis, including hs-CRP) will be performed during study visits at Weeks 12, 16, 20, and 26/Premature Discontinuation, and urinalysis will be performed at Weeks 12, 20, and 26/Premature Discontinuation.

AEs will be collected during the study and for 70 days after the last study drug administration.

Crohn's Disease Activity Index (CDAI) will be obtained during the Screening Period and at Weeks 0, 2, 4, 6, 8, 12, 16, 20, and 26/Premature Discontinuation. If the subject doses onsite then the CDAI will also be completed at Weeks 10, 14, 18, 22, and 24. The inflammatory bowel disease questionnaire (IDBQ) will be administered at Weeks 0, 4, 8, and 26/PD.

Subjects should adhere to the required visit schedule. Study visits should occur within the ± 3 day visit window. The Baseline visit at Week 0 should occur within 35 days of the Screening visit.

Diagnosis and Main Criteria for Inclusion/Exclusion:

Main Inclusion:

1. Male or female of Chinese descent with full Chinese parentage 18 to 70 years (inclusive) of age at Baseline (Week 0).
2. Confirmed diagnosis of Crohn's disease for at least 3 months prior to Baseline (Week 0). Appropriate documentation of biopsy results consistent with the diagnosis of CD, in the assessment of the Investigator, must be available.
3. Subject has hs-CRP ≥ 3 mg/L in all laboratory measurements during the Screening Period.
4. Crohn's Disease Activity Index (CDAI) ≥ 220 and ≤ 450 at Baseline (Week 0) despite concurrent or prior treatment with an adequate course, in the opinion of the investigator, of at least one of the following (oral corticosteroids or immunosuppressants or both as defined below):
 - Subjects taking oral corticosteroids, excluding budesonide:
 - Oral corticosteroid dose must be ≤ 20 mg/day (prednisone or equivalent);
 - For subjects with a dose > 10 and ≤ 20 mg/day, dose has been stable for at least 7 days prior to Baseline and the duration of the current steroid course has been at least 14 days prior to Baseline.
 - For subjects with a dose ≤ 10 mg/day, dose has been stable for at least 10 days prior to Baseline (Week 0) and the duration of the current steroid course has been at least 14 days prior to Baseline (Week 0).
 - Subjects taking oral budesonide:
 - Dose must not exceed 9 mg/day;

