For all variables (discrete/categorical/response variables and continuous variables), except for the endpoint defined for dose-escalated subjects only, the following rules will be used for the LOCF approach:

1. Baseline and pre-baseline values will not be used to impute the missing post-baseline values.
2. Missing values after Study Day 1 will be imputed using the latest non-missing values after Day 1 and prior to the missing value.
3. For subjects who dose-escalate to OL adalimumab 80 mg eow, the last non-missing value before dose escalation will be used for LOCF values at the following visits.

For the endpoints defined for dose-escalated subjects only, the last non-missing value through the entire study will be used for LOCF values at the following visits.

Observed Case (OC)

Observed case analysis will be performed such that missing values will not be imputed. Data from subjects who dose-escalate to OL adalimumab 80 mg eow will be considered missing after the point of dose escalation. These data will not be imputed and will not be included in the numerator or denominator.

Imputation of Missing Dates

For baseline, efficacy, and safety parameters, if the day and/or month are missing, the following conventions will be used to impute the missing dates:

- 01 for missing start day
- End of month for missing end day
- January 1st for missing start month
- December 31st for missing end month

Rule for CDAI Calculation

Up to 14 day of diaries will be recorded in eCRF or CDAI calculation for each visit. Diary entries will be evaluated for the CDAI calculation for each visit. For each CDAI subscore, the available scores from the most recent diary days (at least 4 days, up to

7 days) prior to actual day of the study visit will be summed, and then multiplied by the corresponding multiplier to get subtotal score. If available diary entries are fewer than 7 days, the subtotal score will be calculated as (summed total available score/number of days) \times 7 \times corresponding multiplier. The three subscores (number of liquid/very soft stools, abdominal pain rating, and general well-being) will then be rounded to one decimal. The final CDAI is rounded to a whole number.

If a subject has fewer than 4 days of diary data, the total CDAI score will not be calculated and will be considered missing.

If a subject has any subscore missing, the corresponding total CDAI score will be missing.

Definition of Clinical Remission

CDAI $<$ 150.

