- Proportion of subjects who achieve CDAI $<$ 150, hs-CRP $<$ 3 mg/L and fecal calprotectin $<$ 250 μ g/g at Week 26 in subjects who achieved clinical response (decrease in CDAI \geq 70 points from Baseline) at Week 8.

Additional secondary endpoints include:

- Proportion of subjects with clinical remission (CDAI < 150) over time.
- Proportion of subjects with CDAI < 150 plus a reduction in hs-CRP of at least 50% from Baseline over time.
- Proportion of subjects with clinical response (decrease in CDAI \geq 70 points from Baseline) over time.
- Proportion of subjects with decrease in CDAI \geq 70 points from Baseline plus a reduction in hs-CRP of at least 30% from Baseline over time.
- Change from Baseline in CDAI over time.
- Change from Baseline in hs-CRP level over time.
- Change from Baseline in fecal calprotectin level over time.

The analysis over time will be performed for the DB placebo-controlled period (Week 0 to Week 4), with comparisons between active treatment and placebo groups. The analysis over time will also be performed for Any Adalimumab set (the entire study on or after the first dose of adalimumab), with only summary statistics for adalimumab treatment.

Exploratory endpoints include:

- Proportions of subjects who achieve CDAI < 150 at Week 26 in subjects who did not achieve clinical response (decrease in CDAI \geq 70 points from Baseline) at Week 8.

For categorical endpoints with comparison between the treatment groups, the difference in proportions of subjects between treatment groups will be analyzed using the CMH test adjusted for stratification variables. Additionally, the CMH based two-sided 95% confidence interval for the difference in proportions will be provided. For categorical endpoints with comparison to the clinically meaningful constant rate, the one sample Exact test will be performed and the two-sided 95% CI will be provided. The NRI imputation method will be used for subjects with missing data at the time point

evaluated. Subjects who dose-escalate will be imputed using NRI for visits after dose escalation. The LOCF method will also be used as the sensitivity analyses.

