Change from Baseline in continuous endpoints will be analyzed using Analysis of Covariance (ANCOVA) model including factor for treatment group, stratification factors and Baseline values. For analyses of changes from Baseline variables, both LOCF and observed case analyses will be performed. The LOCF analysis is considered primary for inferential purposes.

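### For change in CDAI and hs-CRP at Week 4, LOCF is the primary analysis although a repeated-measures model on the Week 2 and Week 4 data would avoid its small, direction-uncertain bias under MAR

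*SAP*

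**What the plan says.** SAP 10.3 analyses continuous change endpoints with an "Analysis of Covariance (ANCOVA) model including factor for treatment group, stratification factors and Baseline values". It adds that "both LOCF and observed case analyses will be performed" and that "The LOCF analysis is considered primary for inferential purposes". Protocol section 8.1.4.2 and the protocol synopsis give the same rule. Neither document plans a repeated-measures model or multiple imputation.

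SAP 6.0 sets the carrying rule: "Missing values after Study Day 1 will be imputed using the latest non-missing values after Day 1 and prior to the missing value". It also says: "Baseline and pre-baseline values will not be used to impute the missing post-baseline values".

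On what is tested, SAP 10.3 says: "The analysis over time will be performed for the DB placebo-controlled period (Week 0 to Week 4), with comparisons between active treatment and placebo groups". For the Any Adalimumab set, results over time are presented "with only summary statistics for adalimumab treatment".

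On what is collected, the protocol synopsis says that CDAI "will be obtained during the Screening Period and at Weeks 0, 2, 4, 6, 8, 12, 16, 20, and 26/Premature Discontinuation". hs-CRP is also drawn at Weeks 0, 2 and 4. Fecal calprotectin has no scheduled sample between Week 0 and Week 4, and SAP Table 5 maps everything from Rx Day 2 to Day 43 to Week 4.

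**The concern.** Carrying the Week 2 value to Week 4 assumes that nothing changes in between. That is doubtful here. Only the adalimumab arm receives active drug at Week 2, so the two arms may move by different amounts between the visits. The plan also produces some of this missingness itself: QuantiFERON is repeated at Week 2, and a positive result leads to withdrawal.

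At stake are the Week 4 estimate and p-value for CDAI and hs-CRP change. SAP 10.4 makes no multiplicity adjustment, so these p-values will be read at a nominal 0.05. The direction of the error depends on which arm loses more subjects, so LOCF cannot be defended as conservative.

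**Working it through.** **1. The plan's own figures.** No effect size, SD or power is stated for any continuous endpoint. The sizing figures that are stated reproduce: Fisher's exact power for 24% against 47% with 100 per arm is 90.7% (stated 90%), and exact power for 52% against 30% with n = 100 is 99.4% (stated at least 99%). Neither depends on this point.

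**2. Where LOCF can alter a tested result.**
- Week 2 CDAI and hs-CRP: there is no earlier post-baseline visit and baseline is never carried, so nothing is imputed.
- Week 4 fecal calprotectin: for the same reason, LOCF, observed case and a repeated-measures model use the same subjects and give the same ANCOVA estimate.
- After Week 4: summary statistics only.
- What remains: CDAI and hs-CRP change at Week 4, in subjects with a Week 2 value and no value on Rx Days 23-36 (SAP Tables 2 and 3).

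**3. Inputs for CDAI.** From the documents: 100 per arm, two post-baseline visits, two-sided 0.05. Assumed, because the documents give no values:
- true Week 4 difference -40; placebo mean change -40 at Week 2 and -60 at Week 4;
- residual SD S = 80; correlation between visits r = 0.7;
- share f of the Week 4 effect already present at Week 2: 0.5, 0.7 or 0.9;
- probability d of having a Week 2 value but no Week 4 value: 2-10%, proportional to exp(Week 2 residual / S), which is MAR.

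**4. Simulation.** There were 4,000 trials per scenario. The repeated-measures estimate is the maximum-likelihood one for two visits: D4 = t + b × D2. Here D2 is the Week 2 treatment effect, and t and b are the coefficients of treatment and Week 2 value in the regression of Week 4 on treatment, baseline and Week 2. Bias in points, range over f (positive is toward the null, negative favours adalimumab, Monte Carlo error about 0.2):

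| Drop-out, placebo/adalimumab | LOCF | Observed case | Repeated measures |
|---|---|---|---|
| 2%/2% | 0.02 to 0.65 | -0.19 to 0.27 | -0.11 to 0.26 |
| 5%/5% | 0.27 to 1.19 | 0.05 to 0.11 | 0.08 to 0.16 |
| 10%/10% | 0.48 to 1.77 | -0.25 to 0.11 | -0.22 to 0.08 |
| 10%/3% | -2.59 to -2.09 | 4.31 to 4.55 | 0.06 to 0.29 |

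**5. Check by formula.** The assumed mechanism raises the mean Week 2 residual of drop-outs by one SD. LOCF therefore shifts an arm's mean by d × [(m2 - m4) + (1 - r)S], where m2 and m4 are that arm's mean changes.
- Placebo: d × [20 + 0.3 × 80] = 44d.
- Adalimumab: d × [(60 - 40f) + 24] = d(84 - 40f).
- Equal drop-out: bias = 40d(1 - f). At d = 0.10 this is 2.0 for f = 0.5 and 0.4 for f = 0.9.
- 10%/3%: bias = 0.03(84 - 40f) - 4.4, which is -2.5, -2.7 and -3.0 for f = 0.5, 0.7 and 0.9.
- Observed case shifts an arm by -rSd/(1 - d) = -56d/(1 - d): -6.2 on placebo and -1.7 on adalimumab, so the bias is +4.5.

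These agree with the table up to Monte Carlo error and the cap on drop-out probability at 1.

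**6. Size against noise.** LOCF bias is at most 1.77/40 = 4% of the effect with equal drop-out and 2.59/40 = 6% at 10%/3%. The latter is 2.59/11.69 = 0.22 of a standard error. Coverage of the LOCF 95% interval is 94.2-95.8%. With no true effect, LOCF rejects in 4.8% of trials at 5%/5%, 4.5% at 10%/10% and 6.1% at 10%/3%. The Monte Carlo standard error is √(0.05 × 0.95/4000) = 0.34%, so only the last exceeds chance.

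**The case against.** The strongest reply is that little is left for LOCF to do. Protocol 5.4.1 requires the Premature Discontinuation procedures within 2 weeks of the last dose, and Table 1 includes CDAI and hs-CRP in them. SAP 6.0 assigns early termination visits to analysis windows. A subject last dosed on Day 15 is due by Day 29; if seen on Day 23 or later, that visit supplies the Week 4 value and nothing is carried. This stands. The rate d above must be read as what is missing after such visits are mapped, and it may be near the low end of the range.

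It is also fair that both documents agree, the rule is fully stated, and an observed-case companion is prespecified. The companion does not settle the matter: with more drop-out on placebo, the two planned analyses err in opposite directions and neither is unbiased under MAR.

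A reader might infer more than the documents support:
- *That all continuous change endpoints are affected.* They are not. Fecal calprotectin, the only continuous key secondary endpoint, is untouched. The primary and binary secondary endpoints use NRI, with LOCF only as a sensitivity analysis.
- *That carrying values forward makes the standard error too small.* Model and empirical standard errors were close (for example 11.72 and 11.79 at 5%/5%, f = 0.5).
- *That the rule against carrying baseline loses subjects whom the new model would recover.* A repeated-measures model of change at Weeks 2 and 4 also gains nothing from a subject with no post-baseline value.
- *That the model is unbiased without conditions.* The simulated drop-out was MAR, which is the condition under which the model is valid.

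**Conclusion.** The point holds in a narrow form, as a low-priority improvement. For between-group change in CDAI and hs-CRP at Week 4, the primary analysis relies on a no-change assumption that the collected data make unnecessary. For CDAI, under the assumed inputs, the bias is about 0-2 points toward the null with equal drop-out and about 2-3 points in favour of adalimumab with higher placebo drop-out, on an effect of 40. That is unlikely to change a conclusion by itself.

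The effect, SD, correlation, Week 2 share and drop-out rates are all assumptions, and the points scale with them. Nothing was computed for hs-CRP; the argument carries over in kind, but its size is unknown. The primary endpoint, the key secondary endpoints, the sample size and the Week 26 analyses are not affected.

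**What to change.** In SAP 10.3, make a repeated-measures model on Weeks 2 and 4 primary for change in CDAI and hs-CRP at Week 4. Include treatment, visit, treatment-by-visit, baseline and the stratification factors, with unstructured covariance, and state that it is valid under MAR. Keep the LOCF and observed-case ANCOVAs as sensitivity analyses. Add a sentence that fecal calprotectin at Week 4 has no earlier post-baseline visit, so its LOCF analysis equals observed case; otherwise a reader may think missing samples were imputed.

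The cost is SAP wording and standard code, with no new data. It is not quite free: protocol 8.1.4.2 carries the LOCF rule too, so the departure needs an entry in SAP 12.1, which already records one change from the protocol. It should be made before database lock, when protocol 8.1 requires the SAP to be final.

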10.4 Handling of Multiplicity

No adjustment for multiplicity will be done.

10.5 Efficacy Subgroup Analysis

The subgroups listed below will be used in subgroup analyses of the primary endpoint.

- Sex (male, female)
- Age (\leq median, $>$ median)
- Baseline fecal calprotectin (\leq median, $>$ median)
- Baseline fecal calprotectin ($\leq 250 \mu\text{g/g}$, $> 250 \mu\text{g/g}$)
- Baseline corticosteroid use (yes, no)
- Baseline immunosuppressant use (yes, no)
- hs-CRP at Baseline (< 10 and $\geq 10 \text{ mg/L}$)
- hs-CRP at Baseline (< 30 and $\geq 30 \text{ mg/L}$)
- hs-CRP at Baseline (\leq median, $>$ median)
- Crohn's disease activity (CDAI ≤ 300 , > 300) at Baseline
- Baseline CDAI (\leq median, $>$ median)
- Weight (\leq median, $>$ median)
- Baseline albumin (\leq median, $>$ median)
- Disease duration (≤ 3 years, > 3 years)
- Disease duration (\leq median, $>$ median)

11.0 Safety Analysis

11.1 General Considerations

Safety analyses will include reporting of adverse events, laboratory, and vital sign measurements. Safety analyses will be carried out using the Safety set for the DB placebo controlled period (Week 0 to Week 4), and will be carried out using the Any Adalimumab set for the DB/OL period of Any Adalimumab (the entire study on or after the first dose of adalimumab up to 70 days after the last dose of adalimumab, or the date subjects initiate adalimumab therapy not supplied in the context of Study M14-233). The safety analyses results through Week 4 will be presented using two treatment groups (i.e., ADA160/80 versus placebo). The safety analysis on the Any Adalimumab set will be presented for all the subjects as one adalimumab treatment group.

Comparisons between active treatment and placebo groups will be performed for the DB placebo controlled period using the safety analysis set. The safety variable will be summarized by treatment according to the treatment a subject actually received. The differences between treatment group and placebo in safety parameters will be evaluated using two-sided tests at the significance level of 0.100.

For the any adalimumab analysis Set, only summary statistics will be provided for adalimumab treatment.

Missing safety data will not be imputed.

11.2 Analysis of Adverse Events

11.2.1 Treatment-Emergent Adverse Events

Treatment-emergent AEs will be summarized separately for the DB placebo-controlled period and for the DB/OL period of Any Adalimumab.

Treatment-emergent AEs during placebo-controlled DB period are defined as events that begin or worsen either on or after the first dose of study drug and up to the first dose of

study drug at Week 4, or within 70 days after the last dose of study drug, or the date subjects initiate adalimumab therapy not supplied in the context of Study M14-233, for subjects who discontinued prior to Week 4. Treatment-emergent AEs during DB/OL period of Any Adalimumab are defined as events that begin or worsen either on or after the first dose of adalimumab in DB or OL period, and within 70 days after the last dose of study drug, or the date subjects initiate adalimumab therapy not supplied in the context of Study M14-233.

An overview of treatment-emergent AEs, including AEs of special interest such as adverse events leading to death and adverse events leading to early termination, AEs by Medical Dictionary for Drug Regulatory Activities (MedDRA version 20.0 or later) preferred term and system organ class, AEs by maximum relationship to study drug, and AEs by maximum severity will be summarized by number and percentage.

The number and percent of subjects experiencing treatment-emergent adverse events will be summarized for the following adverse event categories. Comparisons of the percent of subjects experiencing an adverse event between adalimumab and placebo during the DB placebo controlled period will be performed using Fisher's exact tests. Only P values < 0.100 when rounded to three digits will be presented.

- Any treatment-emergent adverse event.
- Any treatment-emergent adverse event with a Reasonable Possibility of being related to study drug by the investigator.
- Any treatment-emergent severe adverse event.
- Any treatment-emergent serious adverse event.
- Any treatment-emergent adverse event leading to discontinuation of study drug.
- Any treatment-emergent adverse event leading to death.
- Any treatment-emergent adverse event of special interest.
- Any deaths.

Adverse events with missing or unknown relationship to study drug will be categorized as having a reasonable possibility of being study drug-related. Adverse events with missing or unknown severity will be categorized as severe.

Treatment-emergent adverse events will be summarized as follows:

- Grouped by System Organ Class and Preferred Term.
- A by-subject listing will be provided.
- Grouped by System Organ Class, Preferred Term and maximum Severity.
- Grouped by System Organ Class, Preferred Term and maximum Relationship to Study Drug.
- Grouped by System Organ Class and Preferred Term with subject numbers.

Treatment-emergent AEs occurring for more than 5% of the subjects in any of the treatment arms will be summarized by MedDRA PT in decreasing frequency of adalimumab treatment arm.

In treatment-emergent AE tables, a subject who reports more than one treatment-emergent AE in different system organ classes will be counted only once in the overall total. A subject who reports two or more different preferred terms which are in the same SOC will be counted only once in the SOC total. A subject who reports more than one treatment AE with the same preferred term will be counted only once for that preferred term using the most extreme incident (i.e., most "severe" for the severity tables and most "related" for the relationship tables).

Adverse events will also be summarized by maximum severity. If a subject has an adverse event with unknown severity, then the subject will be counted in the severity category of "unknown," even if the subject has another occurrence of the same adverse event with a severity present. The only exception is if the subject has another occurrence of the same adverse event with the most extreme severity – "Severe." In this case, the subject will be counted under the "Severe" category.

Adverse events will also be summarized by maximum relationship to study, as assessed by the investigator. If a subject has an adverse event with unknown relationship, then the subject will be counted in the relationship category of "unknown," even if the subject has another occurrence of the same adverse event with a relationship present. The only exception is if the subject has another occurrence of the same adverse event with a relationship assessment of "Reasonable Possibility." In this case, the subject will be counted under the "Reasonable Possibility" category, respectively.

Treatment-emergent AEs will be summarized for any adalimumab set by event rate per 100 patient-years, defined as

$$100 \times \frac{\text{Number of TEAEs}}{\text{Total Patient Years}}$$

where total patient years is defined as the sum of the study drug exposure of all subjects, as defined in an earlier section, normalized by 365.25, and rounded to 1 decimal place.

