3.4 Safety Information

Adalimumab therapy has a well-established and well-described safety profile based on extensive post-marketing experience and continued clinical trial patient exposure since the first approved indication in 2002 for RA. A detailed discussion of the pre-clinical toxicology, metabolism, pharmacology and safety experience with adalimumab can be found in the current Investigator's Brochure. AbbVie is committed to continue to collect safety information including those events that may occur in this trial in order to confirm this established safety profile and to identify any unknown potential adverse reactions, rare events and those events with a long latency. AbbVie is participating in a United States Food and Drug Administration (FDA)-requested, TNF inhibitor class wide exploration of the rare appearance of malignancy in patients who are 30 years of age or younger at the time of diagnosis. The risk of malignancy in this age group has not been established and is difficult to study due to its rarity. AbbVie appreciates your attention to the additional reporting requirements needed in this unlikely event, outlined in Section 6.1.5 under Adverse Event Reporting.

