4.0 Study Objectives, Design and Procedures

4.1 Objectives

The primary objective of this study is to assess the efficacy and safety of adalimumab in inducing (at Week 4) and maintaining (at Week 26 in Week 8 responders) clinical remission, defined as Crohn's Disease Activity Index (CDAI) < 150, in Chinese subjects with moderately to severely active CD and elevated hs-CRP.

Additional objectives are to assess the effect of adalimumab treatment on other efficacy outcomes, including clinical response, steroid free remission, and improvement in quality of life.

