11.3 Analysis of Laboratory Data

Changes from baseline in continuous laboratory parameters will be summarized for each visit. The mean change from baseline will be compared between treatment groups (ADA 160/80 versus placebo) at each time point during the DB placebo-controlled period on the Safety Analysis set. Summaries of mean changes from baseline will be provided on the Any Adalimumab set for the adalimumab treatment.

Mean changes from baseline to post-baseline visits will be summarized with the baseline mean, the visit mean, change from baseline mean, standard deviation and median. The treatment group differences for mean changes from baseline will be analyzed using a one-way ANOVA and between group mean change from baseline with the 95% confidence interval, standard error, and *P* value will be presented.

Shift tables from baseline to the final value according to the normal range will be provided for each hematology, clinical chemistry parameter and urinalysis parameter (specific gravity and pH only).

For selected laboratory parameter with Common Toxicity Criteria (CTC), frequencies and percentages of subjects with post baseline lab values that are Grade 3 or above according

to the CTC toxicity criteria Version 3.0 (or later) will be summarized. Comparisons of the percentage of subjects experiencing a value meeting the criteria between treatment groups will be performed using Fisher's exact tests. Only P values ≤ 0.100 when rounded to three digits will be presented. A separate listing will be provided that presents all of the subjects and values that are CTC toxicity Grade 3 or above. For each of these subjects, the whole course of the respective parameter will be listed.

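### The Week 0-4 adverse event and Grade 3+ laboratory comparisons are filtered by p-value and carry no risk difference or confidence interval, so the output does not show how large an excess the data still allow

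*SAP*

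**What the plan says.** SAP 11.1 limits the placebo comparison of safety to Week 0-4, shown as two treatment groups, and says that differences in "safety parameters will be evaluated using two-sided tests at the significance level of 0.100". After that, everyone who has received adalimumab is presented as a single group with summary statistics only.

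SAP 11.2.1 lists eight overview categories, from any treatment-emergent event to any death. For these, "The number and percent of subjects experiencing treatment-emergent adverse events will be summarized for the following adverse event categories". The comparison "between adalimumab and placebo during the DB placebo controlled period will be performed using Fisher's exact tests", followed by the display rule "Only P values < 0.100 when rounded to three digits will be presented". Event tables by system organ class, preferred term, severity and relationship are also planned, with a by-subject listing.

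SAP 11.2.2 specifies number and percentage for each category of special interest. It does not itself mention a test or a p-value.

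SAP 11.3 uses Fisher's test for Grade 3+ laboratory values, with a slightly different cut-off: "Only P values ≤ 0.100 when rounded to three digits will be presented".

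None of these sections plans a risk difference, risk ratio or interval for a proportion. By contrast, SAP 11.3 and 11.4 give between-group 95% intervals for mean changes in laboratory values and vital signs, and SAP 10.2 and 10.3 give CMH-based 95% intervals for differences in efficacy proportions.

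**The concern.** Safety belongs to the primary objective: "The primary objective of this study is to assess the efficacy and safety of adalimumab" (SAP 4.1). Placebo subjects receive adalimumab from Week 4 (SAP 4.2), so Weeks 0-4 are the only randomised, placebo-controlled safety evidence that the trial will produce.

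In that comparison the only inferential output for event proportions is a p-value shown when it is small and omitted otherwise. An omitted value does not separate p = 0.101 from p = 1.0. With about 100 subjects per arm, moderate excesses in uncommon events will often fall on the omitted side, and the planned tables carry nothing to show how imprecise the comparison is. Mean laboratory changes, which also come from the safety analysis, do get an interval. The event proportions are therefore treated less informatively than the rest of the SAP, with no reason given.

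**Working it through.** **Inputs from the documents.** 100 subjects per arm (SAP 4.3); two-sided Fisher's exact test (SAP 11.1, 11.2.1); p-value printed if it is below 0.100 after rounding to three digits, that is p < 0.0995 (SAP 11.2.1).

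**Inputs assumed.** All 100 per arm are treated and followed to Week 4. The documents give no adverse event rates, so a range is used.

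**Method.** For each of the 101 × 101 outcome pairs (a events on adalimumab, b on placebo), take the two-sided Fisher p-value: the sum of all hypergeometric probabilities, given a + b, that do not exceed that of the observed table. Then

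P(withheld) = 1 − Σ Bin(a; 100, pA) × Bin(b; 100, pP), summed over the pairs whose p-value is printed.

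**Check against the plan's own figure.** The same enumeration at 24% vs 47% and the 0.05 level gives 90.7% power. SAP 4.3 states 90%, so the method reproduces it. The documents state no power or precision for adverse events.

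**Chance that the p-value is withheld**

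| Placebo | Adalimumab | Withheld |
|---|---|---|
| 1% | 4% | 82% |
| 2% | 6% | 74% |
| 5% | 10% | 72% |
| 20% | 30% | 57% |
| 0% | 5% | 44% |
| 10% | 20% | 43% |
| 5% | 15% | 29% |
| 10% | 25% | 15% |
| 20% | 40% | 9% |

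With equal rates between 1% and 40%, a p-value is printed only 0.3% to 7.3% of the time, so the test is conservative against its nominal 10%.

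**Worked example, 8 vs 2.** With 10 events in total, the hypergeometric probabilities of 8, 9 and 10 on adalimumab are 0.04103, 0.00847 and 0.00077, and those of 2, 1 and 0 are the same by symmetry. p = 2 × (0.04103 + 0.00847 + 0.00077) = 0.1005, which rounds to 0.101, so nothing is printed.

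Newcombe 95% interval: the Wilson limits are 0.0411 to 0.1500 for 8/100 and 0.0055 to 0.0700 for 2/100. The difference is 0.06.
- Lower limit: 0.06 − √[(0.08 − 0.0411)² + (0.0700 − 0.02)²] = 0.06 − 0.0634 = −0.3 points.
- Upper limit: 0.06 + √[(0.1500 − 0.08)² + (0.02 − 0.0055)²] = 0.06 + 0.0715 = +13.1 points (limits computed unrounded).

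**Other splits that print no p-value, same formulas**

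| Adalimumab vs placebo | p | Difference, points (95% CI) |
|---|---|---|
| 4 vs 0 | 0.121 | +4.0 (−0.4 to +9.8) |
| 6 vs 1 | 0.118 | +5.0 (−0.5 to +11.5) |
| 11 vs 4 | 0.105 | +7.0 (−0.5 to +15.0) |
| 30 vs 20 | 0.141 | +10.0 (−2.0 to +21.7) |

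The fewest adalimumab events that would print a p-value are 5 against 0 on placebo, 7 against 1, 9 against 2, 13 against 5 and 20 against 10.

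**The two cut-offs.** A p-value that rounds to exactly 0.100 is printed under 11.3 and not under 11.2.1. This will seldom matter in practice, but the two rules do differ.

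**The case against.** The strongest reply is that little is actually concealed. Number and percentage by arm appear whatever the p-value, by-subject listings are planned, and Grade 3+ values are listed with their full course. Every split above would be visible, and a reader could compute the interval from it. A 0.100 cut-off is looser than the 0.05 used for efficacy and can be defended as a signal flag across many rows. The low power comes from 100 per arm and four weeks, and a change of display cannot alter that. All of this stands, and it makes the point one of reporting.

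A reader might go further and infer that real harms will usually show as a blank and be taken as no difference. The documents do not support that. Only the p-value is withheld; larger excesses are more likely than not to print one; and no passage infers safety from a non-significant result.

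A reader might also join the safety objective to Protocol 3.4, which speaks of collecting events "including those events that may occur in this trial in order to confirm this established safety profile". That sentence is a general sponsor commitment in the background section. It goes on to include identifying unknown reactions and rare events, and it sets no decision rule for the Week 0-4 comparison.

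Nor does the display rule clearly extend to each special-interest category. The Fisher wording in 11.2.1 attaches to the eight overview rows, 11.2.2 asks only for number and percentage, and the general sentence in 11.1 is ambiguous on this.

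What the reply does not meet is that the SAP leaves the size and precision of the difference for the reader to derive, in the one randomised safety comparison, while supplying it for mean changes and for efficacy.

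**Conclusion.** The point holds as a gap in what is reported. For the adverse event overview rows and the Grade 3+ laboratory parameters in Weeks 0-4, the SAP plans a significance-filtered p-value and no effect estimate or interval.

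How often the p-value is withheld depends on the true rates. In the scenarios tried it is the likelier outcome for small excesses in uncommon events (82% at 1% vs 4%) and for a 10-point excess over 20% (57%). It is the less likely outcome for 0% vs 5% (44%) and 10% vs 25% (15%). Among the splits worked through, results with no printed p-value remain compatible with excesses of about 10 to 22 points.

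These figures rest on 100 treated per arm, no dropout before Week 4 and assumed event rates. They do not show that harms are hidden or that the sponsor would claim safety from non-significance. The change is worth making because it is cheap and concerns the only placebo-controlled safety data.

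**What to change.** In SAP 11.1, 11.2.1 and 11.3, for the Week 0-4 Safety set:

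- Report the risk difference (adalimumab minus placebo) with a two-sided 95% Newcombe or Miettinen-Nurminen interval for each of the eight overview rows and each Grade 3+ laboratory parameter. Preferably do the same in 11.2.2 for special-interest categories with at least one event.
- Label these intervals as descriptive and not adjusted for multiplicity.
- Print all of the p-values or none. This also removes the mismatch between the two cut-offs.

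The cost is SAP wording and an extra column in tables already planned, with no new data, subjects or procedures. Tables become wider and intervals for rare events will be wide. The change does not raise power; it makes the imprecision visible.
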